In an initial pilot study, an irrigated radiofrequency catheter (Celsius Thermocool F-Curve RF catheter, Biosense-Webster, Inc., Diamond Bar, California) was used in 20 patients with ischemic or non-ischemic ventricular dysfunction, who were scheduled to receive an ICD for either i) secondary prevention, or ii) primary prevention + inducible VT by programmed ventricular stimulation at the time of ICD implantation ([name], unpublished observation). Although we have favorable single-operator, single-center safety data in another RSDN trial, preliminary review of the six-month renal ultrasound data provided a higher than expected event rate of renal artery stenosis. As such, the protocol has been amended to allow for the use of a dedicated renal sympathetic denervation catheter system: the Vessix™ Renal Denervation System (Boston Scientific, Quincy, Massachusetts).

4. SCHEDULE OF TREATMENT AND TESTS:

TABLE 1:

	Baseline	Procedure*	Discharge	1, 6,12,18,24,36 months**
Type of visit	Office	Hospital		Office
Informed Consent	X			
Brief History & Physical	X			X
Blood Laboratory Testing: CBC, Electrolytes, BUN/ Creatinine, BNP	X			X (6, 12, 24, 36m)
Blood for Renal Hormones (OPTIONAL*)	X			X (12m)
TTE	X			X (12 m)
Renal Angiography		X		
Ultrasound or MR/ CT Angiography				X (6 m)
Randomization		X		
Renal Sympathetic Denervation		X		
ICD Interrogation	X			X
EKG	X			X (12m)
Office BP Measurements (including orthostatic BPs)	X			X
Medications	X		X	X
Adverse Events		X	X	X

* Hormonal measurements are optional in cases where the cost would be prohibitively burdensome to patients or hospital/clinic facilities are not available to allow for their measurement.

** - Visit windows – 1 Month (\pm 14 days); 6, 12, 18, 24, 36 Months (\pm 30 days)

5. ENDPOINTS:

5.1 PRIMARY ENDPOINT:

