9.2 POST-PROCEDURE

9.2.1 POST-PROCEDURE FOLLOW UP

- All patients will be monitored to verify vascular hemostasis prior to discharge from the hospital.
- All patients will receive either oral aspirin (81-325 mg QD) or clopidogrel (75 mg QD) or warfarin or one of the NOACs (dabigatran, rivaroxaban, Apixaban) for at least 1 week upon discharge.
- Medication and adverse event review will be performed prior to discharge.
- Complications including vascular, stroke, heart failure etc., and presence of ventricular arrhythmias will be documented.
- ICD programming: (see below section 9.2.3)
- The total number of episodes of VT, ATP, and Shocks will be documented at all visits.
- The follow-up includes:
 - 1 Month (\pm 14 days):
 - History and Physical
 - ICD interrogation
 - Office BP measurements (x2) including orthostatics
 - Review of Medications and Adverse events
 - 6 Months (\pm 30 days):
 - History and Physical
 - ICD interrogation
 - Office BP measurements (x2) including orthostatics
 - Lab tests (CBC, Electrolytes, BUN/Cr)
 - BNP Level

- Review of Medications and Adverse Events
 - Repeat Renal Ultrasound or MR/CT Angiography
- 12 Months (\pm 30 days):
 - History and Physical
 - ICD interrogation
 - EKG
 - Office BP measurements (x2) including orthostatics
 - Lab tests (CBC, Electrolytes, BUN/Cr)
 - Blood for Renal Hormones (OPTIONAL)
 - BNP Level
 - Review of Medications and Adverse Events
 - Repeat TTE
- 18 Months (\pm 30 days):
 - History and Physical
 - ICD interrogation
 - Office BP measurements (x2) including orthostatics
 - Review of Medications and Adverse Events
- 24 Months (\pm 30 days):
 - History and Physical
 - ICD interrogation
 - Office BP measurements (x2) including orthostatics
 - Lab tests (CBC, Electrolytes, BUN/Cr)
 - BNP Level
 - Review of Medications and Adverse Events
- 36 Months (\pm 30 days):
 - History and Physical
 - ICD interrogation
 - Office BP measurements (x2) including orthostatics
 - Lab tests (CBC, Electrolytes, BUN/Cr)
 - BNP Level
 - Review of Medications and Adverse Events

Patients will be followed for a maximum of 36 months until the final patient reaches the 18 month follow-up time point. Once the final patient reaches the 18 month follow-up time point, all follow-ups will cease.

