10.6 POWER AND SAMPLE SIZE

Power for this study was determined based on the following operating characteristics: (a) two sided type I error fixed at 0.0492, assuming one interim analysis, (b) 85% power, (c) minimum follow-up of 18 months, (d) 18-months event rate in the ICD alone group of 19% (e) expected 18-month relative rate reduction in the ICD + RSDN group of $\geq 40\%$, accrual period of 48 months and non-uniform accrual.

Under the above assumptions it is estimated that 70 events (or 462 patients) will be required to detect a relative decrease in the relative event rate reduction requiring any ICD therapy $\geq 40\%$ in the ICD + RSDN compared to the ICD alone group (19% vs. 11.4%) (Lachin, 1981).

Lost to Follow Up: The term "lost to follow-up" is used to define an individual who has withdrawn consent to be in the study or who can no longer be located or assessed. Such individuals represent those for whom primary outcome assessment is no longer possible. Since the primary outcome will be assessed by interrogating the ICD and since patients come back to

the hospital for regular check we do not anticipate a high rate of lost to follow-up. The estimated sample size accounts for 5% attrition due to withdrawal of consent.

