the interaction between the indicator for treatment group and log (t) in a Cox proportional hazards regression model that also includes the main effect for the randomization group. The final analysis will be based on a two tailed 0.0492 level test.

Analysis of Secondary End-points: All continuous variables will be analyzed using mixed effects models (Bagiella et al. 2000; Diggle et al. 1994; Laird and Ware 1982). Log-transformations will be used, if necessary to normalize the variables or stabilize the variance. For binary and discrete outcomes we will use generalized estimating equations (GEE) (Liang and Zeger 1986; Miller et al. 1993; Zeger and Liang 1986) to fit logistic or log-linear models that account for the dependency of the repeated measures.

Missing Data: For participants who withdraw consent to participate we will use all the information available up to the time of withdrawal. For the purpose of the primary analysis these patients will be censored at the time of withdrawal if they have not experienced the primary event. For all other variables, if the data are missing at random (MAR), that is, the probability of being missing depends only on observed values (Little and Rubin 1987), then likelihood-based methods such as mixed-effects models will be used for analysis without bias. If the fraction of missing data is small we expect that even non-ignorability can have only little effect on the final estimates. If the extent of missingness is large compared to the effect size, we will use the multiple imputation procedure proposed by Rubin (1997) and Little (1996).

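### Withdrawals are censored at the withdrawal date rather than at the last ICD interrogation, and no exit or close-out read is planned, so unread device time counts as event-free; the effect on the primary result is small

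*Combined protocol and SAP*

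**What the plan says.** - **Ascertainment.** Section 10.6 expects little loss to follow-up: "Since the primary outcome will be assessed by interrogating the ICD", and patients return for regular checks. Under 5.1, 10.3 and 10.8 an event is ATP or a shock, or incessant VT.
- **Schedule.** After baseline, Table 1 in Section 4 places the ICD interrogation at "1, 6,12,18,24,36 months", and 9.2.1 repeats those visits. The windows are ±14 days at month 1 and ±30 days afterwards. Neither place, nor 10.8 or 11.4, lists an interrogation at withdrawal or closure. Remote transmission is not mentioned.
- **Censoring at withdrawal.** Under Missing Data, 10.8 uses all information available up to withdrawal, and then "these patients will be censored at the time of withdrawal if they have not experienced the primary event".
- **Lost patients.** Section 10.6 also counts patients who cannot be located or assessed as lost. The censoring rule in 10.8 covers consent withdrawal only.
- **End of study.** Section 9.2.1 follows patients for up to 36 months, then: "Once the final patient reaches the 18 month follow-up time point, all follow-ups will cease".
- **Analysis window.** Section 10.8 censors event-free patients at the end of an 18-month period. Section 10.6 plans on "b) 85% power, (c) minimum follow-up of 18 months", which, with 48 months of accrual and the 36-month maximum in 9.2.1, suggests that later time counts as well. The design paragraph of the Protocol Summary gives a third period, 12 months.

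**The concern.** A patient who withdraws at month 11 was last read at month 6. The rule credits five more event-free months, although ATP in that interval may have gone unnoticed and no one is asked to read the device. The Kaplan-Meier risk sets and the hazard denominator then contain time in which device-treated events could not be seen. Event rates are pulled down, and the treatment comparison tilts if withdrawal differs by arm. That is possible here: the operator knows the allocation (9.1.3), and 11.4 lets investigators withdraw subjects for safety or compliance.

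Study closure can have the same effect on a larger scale. A patient at month 35 when follow-up stops was last read at month 24. Whether this touches the primary endpoint depends on the analysis window. It does touch VT burden, ICD storm, and appropriate and inappropriate therapy, which have no stated 18-month limit.

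**Working it through.** **Inputs.** From 10.6: "two sided type I error fixed at 0.0492, assuming one interim analysis"; 85% power; "18-months event rate in the ICD alone group of 19" per cent, against 11.4% with RSDN; 48-month accrual of unstated shape; 5% attrition; "70 events (or 462 patients) will be required". Allocation is 1:1, so 231 per arm. My assumptions: exponential event times, visits on nominal dates, withdrawal uniform over months 0 to 18, and an unstratified log-rank test.

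**Hazards.** Control: −ln(0.81)/18 = 0.01171 per month. RSDN: −ln(0.886)/18 = 0.00672. HR = ln(0.886)/ln(0.81) = 0.574, and |ln HR| = 0.554.

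**The plan's own figure.** 462 × (0.19 + 0.114)/2 = 70.2, so 70 is the event count expected by month 18. It does not follow from the stated power. Schoenfeld's formula gives 4 × (1.967 + 1.036)² / 0.554² ≈ 118 events, and 70 events give about 64% power. That shortfall is a separate matter. It is relevant here because 118 events divided by a mean event probability of 0.256 (uniform accrual, follow-up capped at 36 months) gives 461 patients before attrition. The event count thus fits an 18-month window, while the patient count fits longer follow-up.

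**Withdrawal gap**
1. The gaps between reads up to month 18 are 1, 5, 6 and 6 months. Mean unread time = (1² + 5² + 6² + 6²)/(2 × 18) = 98/36 = 2.72 months, about 30% of the mean 9 months credited to a withdrawing patient.
2. 462 × 0.05 = 23.1 patients, and 23.1 × 2.72 ≈ 63 patient-months.
3. The chance that a withdrawing patient has an unread first event is the mean over withdrawal time w of exp(−λ·last read) − exp(−λ·w): 0.0288 for control and 0.0173 for RSDN. With 231 × 0.05 = 11.55 withdrawals per arm, that is 0.33 + 0.20 = 0.53 events.
4. Expected first events per arm = 231 × [(1 − p) × F + p × (1 − F/(18λ))], where p is the withdrawal fraction and F the 18-month risk. At 5% in both arms: 42.8 + 25.7 = 68.5.
5. In a 4,000-replicate simulation, the HR was 0.571 and power 62% under all three rules: the text's rule, an exit read, and censoring at the last interrogation. At 10% attrition, 1.06 events are missed.
6. Unequal withdrawal, assumed 5% control and 15% RSDN: missed events are 0.33 of 42.8 (0.8%) and 0.60 of 24.4 (2.5%). The rate ratio becomes 0.574 × 0.975/0.992 ≈ 0.565, a shift of about 0.01. The simulation agrees: 0.557 under the text's rule, 0.566 with last-interrogation censoring, 0.567 with an exit read.

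**Closure gap, only if time after month 18 is analysed.** Assume uniform accrual over 48 months, closure at month 48 + 18 = 66, and no withdrawal.

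| Month at closure | Share | Last read | Mean gap |
|---|---|---|---|
| 36 (cap) | 30/48 = 62.5% | 36 | 0 |
| 24 to 36 | 12/48 = 25% | 24 | 6 months |
| 18 to 24 | 6/48 = 12.5% | 18 | 3 months |

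- 37.5% of patients (462 × 0.375 ≈ 173) end between visits, with a mean gap of (25 × 6 + 12.5 × 3)/37.5 = 5.0 months, or about 866 patient-months. That total includes patients who have already had a first event.
- Unread first events, as patients × event-free at last read × mean event probability in the gap. Control: 57.75 × 0.755 × 0.0671 + 28.875 × 0.81 × 0.0343 = 3.7. RSDN: 57.75 × 0.851 × 0.0393 + 28.875 × 0.886 × 0.0199 = 2.4. Total 6.2 of 118.4 (5.2%).
- Power = Φ(√d/2 × 0.554 − 1.967) falls from 85.3% to 83.4%. Crude rates are about 5% too low in both arms, so the HR is 0.573 instead of 0.574.
- Linear accrual shapes: 3.0 of 126 events unread if front-loaded (power 87.5% to 86.7%), and 9.3 of 110 if back-loaded (82.8% to 79.4%).

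**The case against.** The strongest reply is that 10.8 censors at month 18, that month 18 is itself a scheduled read, and that follow-up stops only when the last patient gets there. On that reading a patient at month 35 loses nothing from the primary analysis. This stands. A reader might infer that the missing close-out read removes primary events in any case, and the documents do not support that. What remains is the visit window. A patient read at month 17 is normally read again at month 24, so only those who reach closure before month 24 are exposed (12.5% under uniform accrual), for at most 30 days each.

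A reader might also infer a material bias in the treatment effect. The figures do not show one: half an event at 5% attrition, and about 0.01 on the HR under a deliberately unequal split.

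Nor can it be said that events in the gap are certain to be lost. Shocks and incessant VT may surface clinically, 10.8 does not forbid using a device read that covers time before withdrawal, and silence about remote transmission does not prove there is none. The plan merely requires no such read.

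Finally, last-interrogation censoring has a weakness of its own. If clinically detected events between reads are counted while event-free patients are cut back to their last read, censoring depends partly on outcome and rates are pushed up. This is fair, and it calls for a sensitivity analysis.

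**Conclusion.** The point holds in a limited form. The stated rule credits withdrawals with time in which ATP and other device-treated events may be unseen, and nothing in the plan closes that interval. At the planned attrition the cost is about 0.5 of about 68 first events, with no visible change in HR or power. A shift of about 0.01 toward RSDN needs strongly unequal withdrawal.

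The closure loss is conditional. It is nil for the primary endpoint under 18-month censoring, apart from the visit window. If all follow-up counts, it is about 6 of 118 first events (3 to 9 by accrual shape) and about 1 to 3 points of power, with the HR essentially unchanged. The device-based secondary endpoints lose the same unread months unless they too are limited to month 18.

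These sizes rest on the stated exponential, withdrawal and accrual assumptions. The documents give neither the accrual pattern nor withdrawal by arm. The change is worth making because the better rule is cheap and data left unread at closure may not be recoverable.

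**What to change.** 1. **Section 10.8.** Censor event-free patients who withdraw or are lost at the date of the last ICD interrogation showing no primary event, or at month 18 if that is earlier and the 18-month window governs. This also gives a date for patients who cannot be located. Keep censoring at the withdrawal date as a sensitivity analysis, because shocks and incessant VT may come to light between reads.
2. **Sections 9.2.1, 10.6 and 10.8.** Reconcile these, and the 12-month period in the Protocol Summary, to one analysis window for the primary endpoint. State the window for each device-based secondary endpoint.
3. **Section 9.2.1.** Request a device read at withdrawal where consent allows. If time after month 18 is analysed for any endpoint, collect a close-out interrogation from patients who are between visits at closure.

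The cost is slightly less credited follow-up, short wording changes in the SAP and in 9.2.1, and up to about 170 close-out device checks under uniform accrual. The number would be higher if accrual is back-loaded and lower if front-loaded.

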10.9 PRIMARY SAFETY ANALYSIS

The primary assessment of safety will be based on the incidence of all serious adverse events over the total duration of study follow-up. The between group comparisons of incidence of serious adverse events will be estimated using the incidence rate ratio and corresponding 95% confidence intervals based on Poisson regression.

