Design:	This study is a prospective, multicenter, single-blinded, randomized (1:1) control trial evaluating the effectiveness of RSDN in the primary prevention of ICD therapy in patients with ischemic or non-ischemic ventricular dysfunction who are to receive an ICD for either i) secondary prevention, or ii) primary prevention + inducible VT by programmed ventricular stimulation at the time of ICD implantation. These patients will be randomized to ICD alone or ICD + RSDN. Subjects will only be eligible for this study if they are \geq 18 years of age and have a history of structural heart disease (post-MI, dilated cardiomyopathy, sarcoid myopathy, hypertrophic cardiomyopathy, etc.), and are planned for ICD implantation for: i. Secondary prevention (e.g.: VT/VF arrest, sustained VT, syncope/inducible VT) ii. Primary prevention + inducible MMVT during induction via ICD lead testing. In addition, eligible patients will have accessible renal vasculature (as determined by renal angiography).
	The patient will be blinded to the results of randomization. Once randomized, study group subjects will undergo a strategy of catheter-based renal sympathetic denervation + ICD implantation (if not already present). Control patients will receive standard ICD implantation alone (if not already present). Follow-up will be conducted in regular intervals over a 12-month period.
Enrollment:	Total: 462 subjects (231 control group, 231 study group)
	An interim safety analysis will be performed after the first 50 subjects (25 control group, 25 study group) have completed their 6-month follow-up visit.
Clinical Sites:	
• Icahn School of Medicine at Mount Sinai• Homolka Hospital, Prague, Czech Republic• Heart Center U SV. Anny Hospital, Brno, Czech Republic• Massachusetts General Hospital• Regional Cardiology, Sacramento, California• Medical University of South Carolina• Florida Hospital, Orlando, Florida

	
 • Other Sites TBD
Time Course:	Enrollment: Over 4 years

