The primary safety objective is to demonstrate that the incidence of serious adverse events (events that cause clinically relevant changes in patient's health, or any event that is life-threatening, results in a fatality, results in permanent disability, requires hospitalization, or prolongs an existing hospital stay) is not increased with the use of the ICD + RSDN compared to ICD alone.

10.5 SECONDARY ENDPOINTS:

The following secondary endpoints will be assessed:

- Appropriate ICD therapy assessed in the full intention-to-treat patient cohort
- Inappropriate ICD therapy
- Number of Hospitalizations for Cardiovascular Causes.
- Total VT burden (Number of episodes).
- All-Cause Mortality.
- The occurrence of ICD storm, defined as ≥ 3 appropriate shock therapies within 24 hours.
- Differences in BUN/creatinine measurements.
- Procedure related adverse events including, but not limited to hematomas, pseudoaneurysms and renal artery stenosis.
- Development of orthostatic hypotension
- 30-day Major Complication Rate defined as death, stroke, MI or any other serious adverse events related to the treatment or procedure within the first 30 days or through hospital discharge (whichever is longer).

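### The single pooled SAE rate ratio in section 10.9 dilutes a moderate first-month excess; ratios for days 0-30 and after day 30 should be reported beside it

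*Combined protocol and SAP*

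**What the plan says.** Section 10.4 sets the primary safety objective: to demonstrate that SAE incidence "is not increased with the use of the ICD + RSDN compared to ICD alone". It gives no margin, test or power.

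Section 10.9 is the only analysis named for that objective: "The primary assessment of safety will be based on the incidence of all serious adverse events over the total duration of study follow-up". The comparison is "estimated using the incidence rate ratio and corresponding 95% confidence intervals based on Poisson regression". No early window or period term is specified.

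Section 9.2.1 fixes the length of follow-up: "Patients will be followed for a maximum of 36 months until the final patient reaches the 18 month follow-up time point". With an 18-month minimum (section 10.6), each patient contributes 18 to 36 months. The Protocol Summary differs: "Follow-up will be conducted in regular intervals over a 12-month period".

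Early harm is covered in other places:
- Section 10.5 lists as secondary endpoints the procedure-related adverse events (the eighth) and a "30-day Major Complication Rate defined as death, stroke, MI or any other serious adverse events related to the treatment or procedure" (the tenth), counted to day 30 or discharge, whichever is later.
- Section 9.3 has adverse events tallied for the DSMB for each 50 patients enrolled.
- Section 9.3.1 stops the trial if severe procedure-related events exceed 15% of the treatment arm.

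**The concern.** RSDN is delivered once, directly after randomisation (section 9.1.3). Several risks listed in section 9.4 (bleeding, dissection, vascular injury, thromboembolism) would be expected mainly around the procedure. The background is different in kind. SAEs include any hospitalisation (sections 9.4.1 and 10.4), the patients have structural heart disease, and such events accumulate over the whole of follow-up.

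A single ratio averages the two. The same harm per patient gives a ratio closer to 1 the longer patients are followed, so the result depends partly on the trial calendar. Section 10.8 checks for a changing treatment effect over time on the efficacy endpoint, through a treatment by log-time term. Section 10.9 has no counterpart for safety, where an effect concentrated in time is easier to foresee.

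At stake is whether the randomised comparison that answers section 10.4 could show a moderate early excess.

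**Working it through.** **No plan figure to reproduce.** Section 10.6 sizes the trial on efficacy only. No power, margin or expected SAE rate is given for safety.

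**Inputs from the documents.** 231 patients per arm (Protocol Summary); 18 to 36 months of follow-up (sections 9.2.1 and 10.6); 48 months of accrual (section 10.6).

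**Assumptions.**
- Background L = 0.2, 0.4 or 0.8 SAEs per patient-year.
- RSDN adds e = 0.05 SAEs per patient in days 0-30, that is 231 × 0.05 = 11.55 extra SAEs.
- Mean follow-up T = 18 months (the minimum) or 32.6 months. The second figure takes accrual as uniform: the first 30 months of entrants get 36 months and the last 18 months of entrants average 27, so (30 × 36 + 18 × 27)/48 = 32.6. Section 10.6 says accrual is non-uniform and gives no pattern.
- All SAEs are counted, with independent Poisson counts.

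**Formulas.** Expected control count C = 231 × L × T. Treatment count E = C + 11.55. Ratio = E/C = 1 + e/(L × T). SE(log ratio) = √(1/C + 1/E). Power is the chance that the two-sided 95% interval excludes 1, by the normal approximation. For days 0-30, T = 30/365.25 = 0.0821 years.

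| L per year | Pooled, 18 months | Pooled, 32.6 months | Days 0-30 |
|---|---|---|---|
| 0.2 | 69.3 v 80.9: ratio 1.17, power 16% | 125.6 v 137.2: 1.09, 11% | 3.8 v 15.3: 4.04, 68% |
| 0.4 | 138.6 v 150.2: 1.08, 10% | 251.2 v 262.8: 1.05, 8% | 7.6 v 19.1: 2.52, 58% |
| 0.8 | 277.2 v 288.8: 1.04, 8% | 502.4 v 514.0: 1.02, 6.5% | 15.2 v 26.7: 1.76, 42% |

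At L = 0.4 the expected 95% intervals are 0.86-1.36 (18 months), 0.88-1.24 (32.6 months) and 1.09-5.85 (days 0-30). The 30-day counts are small, so I checked them with an exact conditional binomial test. Power is then 72%, 54% and 38% for L = 0.2, 0.4 and 0.8, close to the table.

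**Shared first-month risk.** Both arms have ICD placement and renal angiography (sections 8 and 9.1.3). If these add 0.03 SAEs per patient to each arm in days 0-30, then at L = 0.4 the counts are 14.5 v 26.1: ratio 1.80, power 43%. With 0.05 they are 19.1 v 30.7: ratio 1.60, power 37%.

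**Larger excess.** With e = 0.15 and L = 0.2, the pooled ratio is 1.50 with 74% power at 18 months and 1.28 with 53% at 32.6 months. Dilution matters for moderate excesses, not for every excess.

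**Late excess.** If the 0.05 arises after day 30 instead, then at L = 0.4 the post-day-30 ratio is 1.09 (T = 18 months) to 1.05 (T = 32.6 months), with power of about 11% and 8%.

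**Shorter follow-up.** With the 12 months of the Protocol Summary and L = 0.4, the pooled ratio is 1 + 0.05/0.4 = 1.125, with about 13% power. The conflict over follow-up does not change the conclusion.

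**The case against.** The strongest reply is that section 10.9 chooses a legitimate quantity. In randomised arms with similar follow-up, the pooled ratio estimates the relative total SAE burden, which matters to patients. It does not become invalid because the hazard ratio varies over time. This stands, and it is why the pooled ratio should stay.

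The plan also watches early harm through the eighth and tenth secondary endpoints, the DSMB tallies and the 15% rule. The harms at issue are those most readily judged procedure-related. A reader might infer that an early excess would go unseen; the documents do not support that. These safeguards still do not replace the missing comparison. The first two are secondary. The eighth endpoint, and the tenth for SAEs other than death, stroke and MI, depend on attribution. Investigators judge causality (section 9.4.6), and the operating physician knows the allocation (section 9.1.3). The 15% rule looks at one arm and at severe procedure-related events only.

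A reader might also infer that a ratio close to 1 would lead the trial to conclude that SAEs are not increased. No decision rule says so. Section 10.9 asks for an estimate and an interval, and an interval such as 0.88-1.24 does not establish absence of an increase. The lack of a margin is a gap in its own right.

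Three further points stand as limits. Every decisive rate is assumed. Shared ICD and angiography risk weakens the 30-day contrast, although implantation may precede randomisation by up to 30 days, which takes part of that risk out of the window. And the safety signal reported in section 3.1, renal artery stenosis in six-month ultrasound data, falls after day 30, so a split there does not sharpen its detection.

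**Conclusion.** The point holds as a limitation of the primary safety comparison. It is not evidence that the plan conceals harm or would reach a false conclusion. For 0.05 extra early SAEs per patient and a background of 0.2-0.8 per patient-year, the pooled ratio is 1.02-1.17 with about 6-16% power, against 1.8-4.0 with about 42-68% in days 0-30. With 3-5% shared first-month SAEs and a background of 0.4, the early ratio is 1.6-1.8 with 37-43% power.

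The direction follows from the formula alone: for a fixed early excess the pooled ratio moves towards 1 as follow-up lengthens. The size rests on rates that the documents do not give. Repeat SAEs within patients would make simple Poisson intervals too narrow, so the power figures are probably optimistic. Even the 30-day comparison is only moderately powered at 231 per arm. Its gain is that an early excess appears as an estimate of visible size.

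**What to change.** In section 10.9, keep the pooled rate ratio and pre-specify the same Poisson model with each patient's follow-up split at day 30 after randomisation, including period and treatment-by-period terms. Report the all-SAE rate ratio with its 95% confidence interval for days 0-30 and after day 30, beside the pooled ratio, wherever the section 10.4 objective is addressed. State in section 10.4 or 10.9 that an interval including 1 does not by itself show that SAEs are not increased.

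The cost is SAP wording and two model terms. Adverse events are already reviewed at the procedure, at discharge and at every visit (section 4, Table 1), and the tenth secondary endpoint already needs event timing to day 30. The price is a wider interval for each period. Late harms, such as renal artery stenosis found at the 6-month imaging, stay diluted in the later period and still rely on the eighth secondary endpoint.

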9.4 RISKS

ICD implantation will occur according to standard procedure, and therefore the risk includes that of a standard ICD implantation. In addition, the risks of the renal sympathetic ablation and renal angiography procedure include:

Common:

- Discomfort at the site of vascular access
- Groin hematoma

Uncommon:

- Bleeding
- Vascular injury
- Renal artery dissection
- Renal artery stenosis or occlusion
- Thromboembolism, including renal infarction and peripheral atheroembolism. This risk is minimized considerably by the short duration of the procedure, as well as the use of a saline-irrigated ablation catheter.
- Risks associated with sedatives/anesthesia.
- Injury to adjacent structures (phrenic nerve, cardiac valves)
- Renal dysfunction potentially needing hemodialysis
- Vascular complications (including pseudoaneurysm, AV fistula requiring surgical intervention)
- Radiation burns
- Pneumonia and/or sepsis
- Death

An adverse event is any undesirable clinical occurrence in a study patient, whether or not it is related to the study intervention. Any condition that was recorded as pre-existing is *not* an AE unless there is a change in the nature, severity or degree of the condition.

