9.4.1 SERIOUS ADVERSE EVENTS

Serious adverse events are defined by FDA regulation as any experience that results in a fatality or is life threatening; results in significant or persistent disability; requires or prolongs a hospitalization; results in a congenital anomaly/birth defect; or represents other significant hazards or potentially serious harm to research subjects or others, in the opinion of the investigators. Important medical events that may not result in death, be life-threatening, or require hospitalization may be considered a serious adverse event when, based upon appropriate medical judgment, they may jeopardize the patient and may require medical or surgical intervention to prevent one of the outcomes listed in this definition. Examples of such medical events include bronchospasm requiring intensive treatment in an emergency room or at home, blood dyscrasias, or convulsions that do not result in inpatient hospitalization.

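### The primary safety rate ratio counts serious arrhythmia and ICD-therapy events with all other SAEs, so arrhythmia benefit can partly offset added serious harm

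*Combined protocol and SAP*

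**What the plan says.** All references are to the combined protocol and SAP.

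- **Objective (10.4).** The trial is to demonstrate that SAE incidence "is not increased with the use of the ICD + RSDN compared to ICD alone".
- **Measure (10.9).** "The primary assessment of safety will be based on the incidence of all serious adverse events over the total duration of study follow-up". The comparison is "estimated using the incidence rate ratio and corresponding 95% confidence intervals based on Poisson regression". No margin, expected SAE rate or safety power is given.
- **What counts.** Section 9.4: "An adverse event is any undesirable clinical occurrence in a study patient, whether or not it is related to the study intervention". Section 9.4.1 makes an event serious if, among other criteria, it is "any experience that results in a fatality or is life threatening" or "requires or prolongs a hospitalization". Section 10.4 adds events that change the patient's health in a clinically relevant way.
- **Exclusions.** None of 9.4, 9.4.1, 10.4 or 10.9 removes ventricular arrhythmias, ICD storm or arrhythmia admissions from the SAE count.
- **Design effect (10.6).** The 18-month rate of first ICD therapy is 19% with ICD alone, and a relative reduction of at least 40% is expected with RSDN.

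**The concern.** A VT/VF episode that is life-threatening, or an arrhythmia admission, is an SAE under these definitions. Such events are also what RSDN is meant to reduce. The same benefit therefore enters twice: once as efficacy, and once as a lower SAE count in the RSDN arm.

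The all-SAE ratio is then centred on 1 when added harm equals serious arrhythmia events prevented, and not when there is no added harm. A ratio near 1 could be read as meeting the 10.4 objective although denervation had added serious events of another kind. Section 3.1 reports more renal artery stenosis than expected in six-month ultrasound data, which led to a change of catheter system. It is therefore worth being able to read harm apart from efficacy.

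**Working it through.** **The plan's own figures.** 19% × (1 − 0.40) = 11.4%, as stated in 10.6. The plan gives no safety calculation to reproduce.

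**Inputs from the documents**
- 231 patients per arm (Protocol Summary)
- 19% and 11.4% with a first ICD-therapy event at 18 months (10.6)

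**Assumed inputs, which the documents do not give**
- b: background non-arrhythmic SAEs per patient, 0.1 to 1.0
- q: share of first endpoint events that are serious, 10% to 100%
- h: excess serious harm per RSDN patient. Controls also have renal angiography, so h means harm beyond angiography.

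**Step 1: prevented events.** 231 × (0.19 − 0.114) = 231 × 0.076 = 17.6 fewer first events in the RSDN arm.

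**Step 2: break-even.** With equal follow-up, expected SAEs are
- control: 231 × (b + 0.19q)
- RSDN: 231 × (b + 0.114q + h)

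The ratio is 1.00 when h = 0.076q, whatever b is.

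| q | break-even h | SAEs per 231 |
|---|---|---|
| 10% | 0.8% | 1.8 |
| 25% | 1.9% | 4.4 |
| 50% | 3.8% | 8.8 |
| 100% | 7.6% | 17.6 |

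**Step 3: one worked case (b = 0.3, q = 50%, h = 10%).** The standard error of the log ratio is √(1/E₁ + 1/E₂). Power is the chance that the lower 95% limit exceeds 1, Φ(ln ratio / SE − 1.96).
- All SAEs: control 231 × 0.395 = 91.2; RSDN 231 × 0.457 = 105.6. Ratio 1.16 (95% CI 0.87 to 1.53), SE 0.143, power 17%.
- Endpoint events excluded: control 231 × 0.3 = 69.3; RSDN 231 × 0.4 = 92.4. Ratio 1.33 (0.98 to 1.82), SE 0.159, power 44%.
- Loss: 44 − 17 = 27 points.

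**Step 4: the range.** Power lost, in percentage points, for h = 10%:

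| b | q = 10% | 25% | 50% | 100% |
|---|---|---|---|---|
| 0.1 | 10 | 26 | 49 | 71 |
| 0.3 | 7 | 15 | 27 | 39 |
| 0.5 | 4 | 10 | 17 | 26 |
| 1.0 | 2 | 5 | 9 | 14 |

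For h = 5% the losses are smaller. Even at q = 100% they are about 15 points at b = 0.3 and 10 at b = 0.5.

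**Step 5: what excluding endpoint events achieves.** At b = 0.3, power is 44% for 10% harm and 15% for 5% harm. At b = 0.5 it is 30% and 11%.

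These figures count first events only. A Poisson count also includes recurrent serious arrhythmias, which would enlarge the offset if RSDN reduces them too.

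**The case against.** **The all-SAE ratio answers the stated question.** Section 10.4 asks about SAEs overall, and 10.9 estimates that. An all-cause comparison of randomized arms needs no judgement about cause, which matters because the operator knows the allocation (9.1.3). This stands, and is a reason to keep the measure.

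**Procedural harm is followed elsewhere.** A reader might infer that denervation could do serious harm unseen. The documents do not support that. Secondary endpoints 8 and 10 cover procedure-related events and 30-day major complications, and BUN/creatinine is also a secondary endpoint. Renal imaging is due at 6 months (9.2.1), investigators grade causality (9.4.6), and severe procedure-related events in more than 15% of the treatment arm end the trial (9.3.1). What remains is that the 10.4 conclusion rests on none of these. Endpoint 10 closes at 30 days or discharge, whichever is longer, and the break-even values above all lie below 15%.

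**ATP or a shock is not an SAE in itself.** The 19% and 11.4% include ATP alone and inappropriate therapy. Full cancellation of 7.6% harm needs every first event to be serious, which is an extreme. This stands: away from break-even the offset is only partial, and it is small when q is low or b is high.

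**There is no formal safety test.** Section 10.9 gives an estimate with a confidence interval, so the power figures describe how often that interval would lie above 1. The plan names no such decision rule.

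**Capture is ambiguous.** Section 9.4.5 lists protocol-defined and serious unanticipated events, so an expected arrhythmia SAE might be thought to fall outside. But 9.4.7 requires expected and unexpected SAEs to be reported, and 10.9 says all.

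**Excluding arrhythmic SAEs could hide proarrhythmia.** One might answer that the primary endpoint captures it. It does not do so fully: it is a first-event endpoint, so recurrent serious VT after a first event would be missed. Replacing the all-SAE measure is therefore not warranted; a second ratio beside it is.

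**Conclusion.** The concern holds in a limited form. The primary safety ratio nets serious arrhythmia benefit against any added serious harm, and no section separates the two. At the design effect the ratio is 1.00 when added harm equals q × 7.6 points, that is 0.8% to 7.6% for q from 10% to 100%. For 10% added harm, the power lost runs from about 2 points (q = 10%, b = 1.0) to 71 points (q = 100%, b = 0.1), with 27 in the middle case.

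The break-even rule follows from the plan's event rates, equal follow-up and first events only. The sizes rest on assumed q, b and h. The finding does not show that the trial would miss procedural harm. It shows that the measure chosen for the primary safety conclusion cannot by itself distinguish no added harm from harm offset by benefit. A margin applied to that ratio alone would not change this, because the ratio itself is netted.

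**What to change.** - **10.9:** keep the all-SAE rate ratio and label it a net measure. Beside it, pre-specify the same Poisson rate ratio without non-fatal SAEs that the Clinical Events Committee adjudicates as ventricular-arrhythmia or ICD-therapy events. Keep all deaths in both.
- **9.3.2:** have the adjudicators masked to treatment arm, which the section does not state. Extend their remit from ICD events to the cause of these SAEs.
- **10.4:** require both ratios to support the conclusion that SAEs are not increased.
- **Reporting:** list the excluded arrhythmic SAEs by arm, including recurrent ones.

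**Cost.** SAP wording, one extra model on data already collected, and some added adjudication. SAEs must be attributed as arrhythmic or not, and the safety result may look less favourable to RSDN. The added comparison still has limited power (44% for 10% harm and 15% for 5% harm at 0.3 background SAEs per patient). The absence of a margin is a separate gap that this change does not close.
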